3.3 Tertiary/Exploratory

Objective	Brief Description/Justification of Outcome Measure	Outcome Measured By	Time Frame
Explore the influence of prosthesis type on the incidence of prosthetic and biologic complications in a private practice setting.	The influence of the prosthesis on both prosthetic and biologic complications has been described in the literature. This analysis will explore therapies and strategies associated with dental implant success and that minimize prosthetic or biologic complications.	The incidence of biologic and prosthetic complications will be determined for each type of prosthesis (described above).	Data are collected at baseline and at the 1-3-year annual follow-up visits.
Explore factors predictive of patient OHRQoL (which includes satisfaction with esthetics and function).	The data will be used to construct models to explore the predictive factors for patient success. Data for model inclusion will include baseline patient specific data, surgical data, and prosthetic follow-up data. Peri-implant health and prosthetic performance will also be included.	The OHRQoL will be used to examine the association between patient/implant/therapy factors and the OHRQoL score.	Data are collected at baseline and at the 1-3-year annual follow-up visits.

4 STUDY DESIGN

- This is a prospective, observational 3-year cohort study of patients who undergo dental implant restoration by practitioners of the National Dental PBRN. Practitioners who restore dental implants will recruit and enroll their patients in this cohort study during the prosthetic phase of implant therapy.
- Approximately 200 practitioners from all 6 Network Nodes (approximately 35 practitioners per Node) will participate in the study, with each practitioner contributing approximately 10 patients and a maximum of approximately 50 implants.
- The patient population will comprise patients who plan to receive dental implant restorations provided by practitioners of the National Dental PBRN. Approximately 1550 patients will be enrolled until approximately 2000 implants are available for longitudinal observation. Implants will be clustered within patients and within approximately 200 dental practitioners across network practices. Each enrolled patient can contribute more than one implant if multiple implants will be restored at the baseline visit.
- Practitioner and practice characteristics from the National Dental PBRN Enrollment Questionnaire will be combined with data collected for this observational study.
- The prospective, observational study design will allow an opportunity to inform our knowledge of parameters for implant success and risk factors for biologic and prosthetic complications associated with implant therapy. The study will describe the implant restorative therapy provided by the practitioners, the incidence and prevalence of biologic and prosthetic complications, and will correlate patient-level factors, prosthetic- and implant-level characteristics with the risk for implant complications and the therapies provided for dental implant complications.
- The baseline data collection will occur at the prosthetic placement visit, at which time patient baseline characteristics, their overall health and oral health status will be collected, and peri-implant hard and soft tissue status and prosthesis data will be captured. Patients will undergo annual follow-up visits at 1, 2, and 3 years (with a preferred target window for each visit ranging from a target date of -30 days to +150 days of the visit following prosthetic placement). During or after follow-up visits, patients will report satisfaction with aesthetics and function and oral health quality of life measures. Reminder emails or texts, if the patient opts into text messaging will be sent to patients who do not complete the surveys. Practitioners will record data on the patients' oral health, peri-implant tissue health, and the implant prosthesis(es), with a focus on biologic and prosthetic complications that have occurred since prosthetic placement.

- Consent will be recorded electronically, and data will be collected via electronic means for the entire study. The consent process and enrollment will be completed at the prosthetic placement visit. Practitioners will provide clinical examination and procedural data electronically via tablets, smart-phones, or computers in-office or post visit at baseline and the 1-, 2-, and 3-year annual follow-up visits. Patient-reported data will be collected via tablets, smart-phones, or computers after in-office visits. To assist with in-office data collection, study practitioners may be offered tablets.
- Dental radiographs of each implant obtained for clinical care purposes will be collected at the following 4 time points: 1) baseline at the prosthetic placement visit, 2) 1-year annual follow-up visit, 3) 2-year annual follow-up visit, and 4) 3-year annual follow-up visit. Radiographs will be digitally uploaded via the study portal.
- Practitioners will submit digital radiographs of each study implant, taken at baseline (after implant prosthetic placement) and at annual follow-up visits 1, 2, and 3 years following prosthetic placement. The radiograph should be void of any identifiers. Radiographs will be uploaded to the centralized study database provided by the NCC. The study team completes the final review to determine whether the radiograph is sufficient quality to be included in the radiograph repository. If the radiograph is insufficient quality, the study team will work with the Node Coordinator to provide feedback, if applicable, and determine whether a higher quality radiograph can be found. Radiographs in the radiograph repository will go through the adjudication process, where trained and calibrated evaluators assess the radiograph for quality and will determine peri-implant bone height measurements and prosthetic fit for each implant.
- Depending on the patient's enrollment date and whether future funding is obtained, a patient may not complete all study visits. If that occurs, the NCC, study team, practitioner, and/or Node Coordinator will reach out to the participants to inform them of the study status and future visits.
- If an implant has been removed since the last study visit, the practitioner will note this in the CRFs. The practitioner will complete the CRFs in relation to the situation prior to removal. No additional study visits will occur for the removed implant.
-

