5.4 Strategies for Recruitment and Retention

5.4.1 *Practitioner Recruitment and Retention*

Node Coordinators from all 6 regions will determine possible interest of dentists by contacting dental practices enrolled in the National Dental PBRN. Practitioner recruitment will be led by the study team in collaboration with Node personnel. Practitioners will be enrolled from all 6 Regional Nodes of the National Dental PBRN. Survey data from the National Dental PBRN showed that 65% of private practitioners reported providing implant therapy within their practices, and 23.7% indicated they routinely provide implant therapy in their practices. The network practitioner database will be used to identify practitioners to recruit for this study.

We will strive to complete patient enrollment within approximately one year. Consequently, it is anticipated that approximately 200 practitioners will be needed to complete patient enrollment during the practitioner-specific enrollment period. Each practitioner may contribute up to approximately 50 implants.

Node Coordinators (NCs) will recruit practitioners from the Network's 6 geographic regions. The recruitment from all Nodes within the Network will capture a cohort of practitioners with a wide geographic distribution. Retention will be an important aspect of the cohort study, and the design of all aspects of the study will take into consideration the burden to the practitioner and the retention of participants. The study team and NCs will maintain efforts to engage practitioners throughout the duration of the study, including addressing practitioner questions and concerns and implementing processes to streamline data collection in dental offices.

For the baseline visit, practitioners will receive \$100 remuneration for each implant where the Practitioner has completed the following: Baseline Characteristics, Mucosal Characteristics, Prosthetics Characteristics Surveys and upload of baseline study implant radiographs. For follow up year 1, year 2, and year 3, practitioners will be remunerated \$25 per implant for the completion of the Annual Follow-up Survey and submission of radiograph(s) for patients.

For the approximately 2000 implants enrolled we budget for 1X\$100 and 3X\$25 for the total of \$350,000. This is a considerable expense but is justified by the importance of continued longitudinal data collection and retention of the practitioners and patients.

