5.4.2 Patient Recruitment and Retention

The target sample size for this observational study is approximately 1550 patients and approximately 2000 implants, clustered within approximately 200 dental practitioners across all 6 Network Nodes. Patients planned for implant prosthetic placement will be recruited by practitioners and/or their office staff over a recruitment period of approximately 12 months. Practitioners will be asked to use a consecutive enrollment strategy. Each practitioner will establish a regular recruitment period (days and/or times) each week that fits the practice and is sufficient to meet enrollment targets. A screening criteria log will be used to record potential patient refusal/non-enrollment and, where allowed, reasons for non-enrollment, during established recruiting periods. Practitioners' recruitment schedules may be adjusted at any time with the consultation of the NC. Each practitioner will be asked to contribute approximately 10 patients, with a maximum of approximately 50 implants per practitioner.

Office staff may provide an information sheet and instruct the patient to discuss the study with the practitioner. All patients presenting at participating Network practices may be considered for eligibility after screening by the practitioners and/or trained office staff. The practitioner or other appropriately trained staff members will ask the patient if the patient wants to enroll in the study, provide the patient with an information sheet if the patient does not already have one, and will obtain the verbal authorization to put their information into the HUB.

Patient retention is important to this study. Patients will be remunerated \$25 for the baseline data collection visit and \$25 for each of the three annual follow-up visits. Payments will be processed for each completed part of the study.

Study practitioners will be contacted prior to each follow-up data collection interval. The NCC will create reports with practitioner and patient windows that can be accessed by NCs. Node personnel will remind practitioners to follow-up with non-responders prior to the close of each data collection window and may use mail, email, telephone and/or text messages to encourage the scheduling of the follow-up visits.

Opportunities for engagement of the practitioners with the study team may be created throughout the study in the form of webinar based continuing education sessions on topics of interest to the practitioners.

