6 STUDY SCHEDULE

Practitioners enrolled in the National Dental PBRN across the six regions who express interest in the study and meet eligibility criteria will be invited to participate. Study information and instructions will be provided to interested practitioners by Node personnel. After practitioners are eligible and enrolled, Practice Training Materials will describe the participant selection procedures, methods for approaching patients and obtaining informed consent, methods for data collection, and other study procedures for the dentist(s) and office staff who will help to execute the study. A summary flow chart will provide an overview of all study visits and study procedures/data collection for each visit. Utilizing a train the trainer model, the NCC will conduct training with the NCs, who will train practices on the EDC. In addition, NCs will conduct in-person or remote protocol and electronic data management system training with practitioners and office staff prior to initiating the study. The training ensures that the practitioner and staff understand the study procedures and receive instruction on the consent process, the electronic data capture system, and the radiographic upload. The NCs will maintain close contact with the practitioners prior to and throughout the study implementation period.

The study schedule will proceed in the following stages on a rolling basis:

- 1) Each region will enroll practitioners into the study to obtain a total of approximately 200 practitioners across all regions. A reasonable balance across regions is preferred but not required;
- 2) Practitioners will complete activities to be deemed research-ready and study-ready;
- 3) NCs will train research-ready and study-ready practitioners and their office staff in the appropriate study procedures; and
- 4) Practices will screen and enroll eligible patients into the study.

The Study Team, NCC and Node personnel will coordinate the launch of the study. For each of the six regions, participating practitioners will be enrolled over a period of approximately 12 months. Practitioners will begin study recruitment as soon as possible following study training with an NC.

An overview of study procedures to be completed at each study visit can be found in Appendix A.

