6.3 Patient Baseline Visit Prosthesis insertion (Visit 1, Day 0)

At the prosthetic placement visit if a patient is eligible and interested in the study, the patient will undergo the consenting process pursuant to overseeing IRB requirements. If an eligible patient wishes to decline participation in the study, this occurrence will be noted in the screening log, and the informed consent process will not be completed.

- Verify inclusion/exclusion criteria and complete the Screening Log
- Obtain and document consent according to regional IRB requirements
- After enrollment procedures have been completed, the patient will:
 - Complete the *Baseline Patient Demographics, Patient Contact survey, and Patient Characteristics Survey*
 - Complete the *Baseline Oral Health Quality of Life Survey (OHRQoL) Survey*

The practitioner will:

- Perform an oral examination and complete the *Baseline Data, the Mucosal and Prosthetics Characteristics Surveys*
- Upload radiographs of the study implants that have been obtained for clinical care purposes

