The unit of analysis for the secondary objectives are at the implant level for the biologic complications and the prosthesis level for the prosthetic complications. All the outcomes are binary outcomes (Y/N), and for primary analysis only the first occurrence will be considered. Multiple implants/ prostheses are clustered within the same patient, and multiple patients clustered within practitioners. To account for these correlations, General Estimating Equations (GEE) will be used to identify practitioner, patient and implant variables that are associated with the complications. A binomial model with a logit link function will be used for these binary outcomes. Separate analyses will be conducted for each complication. The variables in table 3 will be considered as potential risk factors.

Secondary analysis will evaluate the association between patient/implant/prosthetic risk factors and the rates of repeated prosthetic complications and the disease progression in biologic complications. For the rates of prosthetic complications, the outcome will be the number (count) of prosthetic complications during the 3-year follow-up period. The unit of analysis will be at the person level, and Poisson models will be used to identify practitioner, patient and prosthesis risk factors that are associated with a higher rate of prosthetic complications. For disease progression in biologic complications, the outcome will be mm bone loss (continuous) over time. Mixed effects model will be used to

account for the longitudinal nature of the data and to identify the practitioner, patient and implant risk factors that are associated with a higher amount of bone loss.

Table 3.

Practitioner level factors	
Number of implants restored per month	biologic and prosthetic complications
Years in practice	biologic and prosthetic complications
Post graduate education	biologic and prosthetic complications
Specialty training	biologic and prosthetic complications
Patient level risk factor	outcome
Age at baseline	biologic and prosthetic complications
Diabetes Mellitus	biologic complications
Smoking status	biologic complications
Medication use SSRI Bone sparing drugs Corticosteroid use	biologic complications
Osteoporosis	biologic complications
Radiation therapy	biologic complications
Periodontitis diagnosis	biologic complications
Gingivitis diagnosis	biologic complications
Parafunctional habits	prosthetic complications
Implant/ Prosthesis level risk factor	

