14.2 Institutional Review Board

The protocol and written information sheet will be submitted to the Central IRB for review and approval. Recruitment materials and all participant materials will undergo local context review by ceding IRBs. Approval of both the protocol and the consent form(s) must be obtained before any participant is enrolled. Any amendment to the protocol will require review and approval by the Central IRB before the changes are implemented in the study.

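### No planned risk-factor model contains Node, although Nodes organise recruitment, training, reminders and data queries, so odds ratios for prosthesis-type factors could be confounded by region (minor)

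*Protocol*

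**What the plan says.** **Organisation by Node.** Section 4 of the protocol says "Approximately 200 practitioners from all 6 Network Nodes (approximately 35 practitioners per Node) will participate in the study". Several activities run through the Nodes:

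- Recruitment (5.4.1): "Practitioner recruitment will be led by the study team in collaboration with Node personnel".
- Training (6): "Utilizing a train the trainer model, the NCC will conduct training with the NCs, who will train practices on the EDC".
- Follow-up (5.4.2): "Node personnel will remind practitioners to follow-up with non-responders prior to the close of each data collection window".
- Data queries (13): Node Coordinators take up discrepancies and missing forms with the practices.

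Equal Node sizes are not imposed. Section 6 says "A reasonable balance across regions is preferred but not required".

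**Analysis.** For the secondary objectives, section 11.3 says "General Estimating Equations (GEE) will be used to identify practitioner, patient and implant variables that are associated with the complications". It names two levels of correlation: implants or prostheses within patient, and patients within practitioner. Table 3 lists the candidate factors at practitioner, patient and implant or prosthesis level, and Table 4 does the same for quality of life. Node or region appears in neither table. It is also absent from the descriptions of the Poisson model, the mixed models and the incidence subgroups.

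**The concern.** This is a non-randomised cohort, so nothing balances Nodes across prosthesis types. Retention type, abutment and material are chosen in the practice, and those choices may follow regional habit. Bleeding on probing and prosthetic complications are recorded by practitioners whom Node staff train, remind and query. If Node is related both to a factor and to the risk or recording of a complication, a model without Node attributes part of the regional difference to the factor.

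Specifying practitioner as the cluster in a GEE addresses the standard errors. It is not an adjustment for a variable that sits above the cluster. The four practitioner factors in Table 3 (implant volume, years in practice, postgraduate education, specialty training) do not identify region.

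The estimates at stake are the prosthesis-type odds ratios, which bear on the secondary objective and on Hypotheses 3 and 4.

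**Working it through.** **The plan's own figures.** The protocol has no figure for Node. The nearest benchmark is Table 2. Take 1400 × 1.4 = 1960 implants in two equal groups, an effective number of 1960 / (1 + 0.4 × ICC), two-sided 5% and 80% power (the power is assumed; section 11.2 does not state it). For ICC 0.1 to 0.5 the detectable values are then:

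- Reference 50%: 56.44% to 56.91% (stated 56.43% to 56.90%).
- Reference 20%: 25.40% to 25.82% (stated 25.40% to 25.81%).

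Table 2 therefore reproduces, and it has no Node component. On the odds-ratio scale its smallest detectable effect at a 20% reference is (0.254/0.746) / (0.20/0.80) = 1.36.

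**Illustration with two blocks of Nodes.** All inputs are assumptions: two equal blocks, 1000 cemented and 1000 screw-retained implants, and no true effect within either block. Let e₁ and e₂ be the cement shares (here e₁ + e₂ = 1) and r₁ and r₂ the complication risks.

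- Risk if cemented = e₁r₁ + e₂r₂
- Risk if screw-retained = (1 − e₁)r₁ + (1 − e₂)r₂
- Odds ratio = odds if cemented / odds if screw-retained

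| Cement share | Risk | Risk, cemented | Risk, screw-retained | Odds ratio |
|---|---|---|---|---|
| 40% v 60% | 17% v 23% | 0.068 + 0.138 = 0.206 | 0.102 + 0.092 = 0.194 | 1.08 |
| 35% v 65% | 15% v 25% | 0.0525 + 0.1625 = 0.215 | 0.0975 + 0.0875 = 0.185 | 1.21 |
| 30% v 70% | 15% v 25% | 0.045 + 0.175 = 0.220 | 0.105 + 0.075 = 0.180 | 1.28 |

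For the last row, (0.22/0.78) / (0.18/0.82) = 0.2821/0.2195 = 1.28.

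The chance that a nominal 5% test rejects follows from z = difference / SE. In the middle row, SE = √[(0.215 × 0.785 + 0.185 × 0.815)/1000] = 0.0179 and z = 0.030/0.0179 = 1.68, so rejection is 39%. With a design effect of 1.3, z = 1.68/√1.3 = 1.47 and rejection is 31%. Over the same two design effects, the first row gives 9–10% and the last 50–61%. A larger design effect from practitioner clustering would lower these rates but would leave the odds ratios as they are.

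**Illustration with six equal Nodes.** Exposure share and risk both rise linearly across Nodes, again with no true effect. There are 2000 implants and the design effect is 1 + 0.4 × 0.3 = 1.12.

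| Exposure share | Risk | Odds ratio | Rejection at 5% |
|---|---|---|---|
| 45–55% | 45–55% | 1.02 | 5% |
| 40–60% | 15–25% | 1.06 | 8% |
| 40–60% | 40–60% | 1.08 | 12% |
| 30–70% | 10–30% | 1.26 | 51% |
| 50% in all Nodes | 30–70% | 1.00 | 5% |

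The last row shows that the bias needs Node to be related to both the factor and the outcome. In both illustrations a Node term returns the odds ratio to 1.00, because all of the confounding was placed at Node.

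**The case against.** **Covariates are often left to an SAP.** Table 3 offers its variables as candidates and does not exclude others, and an SAP could add Node. That is fair, but section 11.3 is specific about its factors and its clustering levels. An SAP that followed it would have no Node term.

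**The documents show no regional difference.** This stands. A reader might infer that regional habits will show up as risk-factor effects. The protocol supports only that they could, and the larger odds ratios above need wide spreads that line up across Nodes.

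**Several pathways are partly closed.** This also stands in part:

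- Much of the patient risk mix is already in Table 3.
- Training starts centrally, because the coordinating centre trains the Node Coordinators, and data entry uses common edit checks.
- Bone loss is read centrally by two calibrated evaluators blinded to each other's measurements, so differential recording is a weak argument for peri-implantitis.
- Consent steps refer to regional rules ("Obtain and document consent according to regional IRB requirements"), but "The protocol and written information sheet will be submitted to the Central IRB for review and approval", and no route from consent procedure to a biased odds ratio is apparent. Consent is not part of this point.

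**Node is not a design stratum.** A reader might take the figure of about 35 practitioners per Node as stratified sampling. The protocol does not say so, and it does not require regional balance. A call to stratify the primary confidence intervals would also gain almost nothing. With risks of 15% and 25% in two equal halves, the between-Node variance is 0.05² = 0.0025 out of 0.20 × 0.80 = 0.16, which narrows the interval by less than 1%.

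**The pooled table ignores the GEE weighting.** An exchangeable working correlation would move weight towards contrasts within practitioner and so reduce the bias somewhat. That is a side effect of an unspecified choice and does not amount to adjustment for Node.

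**The stakes are limited.** Hypotheses 3 and 4 match an exploratory objective in section 3.3. The same prosthesis factors do, however, also serve the secondary objective through Table 3.

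**Conclusion.** The concern holds as a minor point. Nodes organise recruitment, practice training, reminders and data queries, and no model or factor table in section 11.3 contains Node. Between-Node confounding of the prosthesis-type odds ratios is therefore left unadjusted, if it exists.

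Under the assumed aligned spreads in two blocks of Nodes, the spurious odds ratio runs from about 1.08 to 1.28. The upper end approaches the 1.36 that Table 2 treats as detectable at a 20% reference. With spreads of 45–55% it is about 1.02. These sizes rest on assumed cement shares and risks, on perfect alignment across Nodes, and on a pooled table without the Table 3 covariates.

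The point applies mainly to bleeding on probing and prosthetic complications. The primary incidence and prevalence estimates and their confidence intervals are not affected.

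**What to change.** In section 11.3, add Node (6 levels, 5 degrees of freedom) as a fixed adjustment covariate in the GEE, Poisson and mixed risk-factor models. Report the estimates with and without Node side by side. Where a complication is rare, state beforehand that Nodes will be grouped or that the Node-adjusted model will serve as a sensitivity analysis. The primary confidence intervals need no change.

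The cost is analysis wording only, since Node is known for every practitioner and about 200/6 = 33 practitioners are expected in each. The drawbacks are the 5 degrees of freedom and sparse cells for rare complications. A Node term also does not remove confounding between practitioners within the same Node, and the report should say so.
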